#### 1. AMENDMENT HISTORY

Amendment No.	Protocol Version No.	Date issued	Author(s) of changes	Details of Changes made
1	1.1	19/05/21	[name]	Change of device

## 2. SYNOPSIS

Measurement of peak knee extensor torque is important following anterior cruciate ligament (ACL) reconstruction. Isometric electromechanical dynamometry (Iso-ED) is the gold standard method of measuring peak knee extensor torque, but access to this equipment is limited due to the associated expense and lack of portability. Inline 'pull-type' dynamometry is an alternative measure that is more affordable, portable and less time consuming, but this device has not been adequately investigated for reliability or validity. This study will investigate the reliability and validity of an inline 'pull-type' dynamometer for measuring peak knee extensor torque in patients following ACL reconstruction. For the reliability study, healthy volunteers will be assessed by two assessors (inter-rater) at the index testing session, with testing repeated by one assessor one week later (test-retest). Validity will be investigated against Iso-ED as the gold standard. The results of this study will help to determine whether inline dynamometry can be recommended as a reliable and valid means of measuring knee extensor torque in clinical practice.

Study Title	Reliability and validity of inline 'pull-type' dynamometry for measuring peak knee extensor torque in patients following anterior cruciate ligament (ACL) reconstruction.
Internal ref. no.	R&D SP0558
Type of study	Clinical investigation of a medical device
Trial Design	Prospective, cross sectional study using a within-participant, repeated measures design.
Trial Participants	Healthy participants recruited from staff at LUH for reliability study Patients who have had ACL reconstruction at LUH for validity study
Planned Sample Size	20 participants for reliability study 44 participants for validity study
Follow-up duration	One week for reliability study No follow up required for validity study
Planned Trial Period	6 months
Primary Objective	To determine the reliability and validity of inline 'pull-type' dynamometry for measuring peak knee extensor torque
Secondary Objectives	To determine comfort levels when testing using different devices
Primary Endpoint	Peak knee extensor torque, recorded in Newton-metres, measured with inline dynamometry and isometric electromechanical dynamometry
Secondary Endpoints	Pain during testing measured with a numerical rating scale
Device Name	KForce Link Cybex HUMAC Norm (CSMI Medical Solutions, Stoughton, MA, USA) dynamometer, using software version Humac 2009.
Manufacturer Name	K-invent
Principle intended use	Force measurement
Length of time use the device has been in use.	Inline dynamometer: 3 years

### 3. ABBREVIATIONS

AE	Adverse event
ADE	Adverse Device Effect
CI	Chief Investigator
CRF	Case Report Form
CRO	Contract Research Organisation
CT	Clinical Trials
CTA	Clinical Trials Authorisation
GCP	Good Clinical Practice
GP	General Practitioner
ICF	Informed Consent Form
ICH	International Conference of Harmonisation
LUHft	Liverpool University Hospitals NHS Foundation Trust
MHRA	Medicines and Healthcare products Regulatory Agency
NHS	National Health Service
NRES	National Research Ethics Service (previously known as COREC)
PI	Principal Investigator
PIL	Participant/ Patient Information Leaflet
R&I	R&I Department
REC	Research Ethics Committee
SAE	Serious Adverse Event
SADE	Serious Adverse Device Effect
SIL	Subject Information Leaflet (see PIL)
SOP	Standard Operating Procedure
TMF	Trial Master File
UADE	Unanticipated Adverse Device Effect

#### 4. BACKGROUND AND RATIONALE

Lower limb strength testing is utilised in various settings including surveillance of uninjured athletes (1), patient monitoring during rehabilitation and determining readiness to return-to-play (RTP) following anterior cruciate ligament reconstruction (ACLR) (2). Knee extensor muscle weakness is associated with an increased risk of re-injury and reduced functional performance following ACLR (3-5) and is a modifiable risk factor for knee osteoarthritis (6). Knee extensor strength deficits may be present in those that pass functional RTP tests (e.g., hop for distance) (5, 7, 8), highlighting the importance of quantifying knee extensor strength specifically.

Isometric electromechanical dynamometry (Iso-ED) is the gold standard method for quantifying knee extensor strength (indicated by peak isometric torque) (9), with hand-held dynamometry (HHD) considered an alternative measure that is more affordable, portable and less time consuming (10). 'Push-type' HHD requires belt stabilisation for stronger subjects (10-13) and demonstrates similar peak isometric torque generating capacity to Iso-ED when performed at approximately 90° knee flexion in healthy volunteers (14). However, peak knee extensor torque occurs at 60-70° knee flexion (15), which is difficult to measure using belt-stabilised 'push-type' HHD due to slippage of the device or a non-perpendicular force being applied to the gauge (16). When compared directly, 'push-type' HHD performed at approximately 90° knee flexion overestimated limb symmetry in subjects with various knee joint impairments and could not be recommended as a direct substitute for Iso-ED at 60° knee flexion (16).

To date, only one study has investigated the reliability and validity of HHD for measuring peak knee extensor torque in patients following ACLR (17). 'Push-type' HHD performed isometrically at 90° knee flexion was shown to have excellent test-retest reliability (ICC: 0.98) and 100% specificity for detecting a limb symmetry index (LSI) >10%, but only moderate to good validity ( $r=0.62$ ) versus isokinetic dynamometry. Although LSI is recommended as an objective, criterion-based guideline for return to running (18) or RTP (2) following ACLR, leg dominance or dysfunction of the reference limb may overestimate the capacity of the side being measured, potentially leading to a premature return to high-risk activities and subsequent re-injury (19). Peak isometric knee extensor torque normalised to body weight is an alternative means of determining whether an individual has achieved target values associated with positive knee-joint function following ACLR ( $\geq 3.0-3.1$  Nm/kg) (20, 21). Mean peak torque values in the aforementioned study were 1.67 ( $\pm 7.4$ ) Nm/kg and 2.03 ( $\pm 7.9$ ) Nm/kg for isometric HHD and isokinetic testing respectively, indicating a lower force generating capacity for 'push-type' HHD. In addition, since the reference values were

obtained isokinetically (60°/sec), it is likely that the validity of 'push-type' HHD would be lower if Iso-ED was used as the reference standard.

Inline dynamometers allow isometric knee extensor torque to be measured at peak angles (i.e., 60-70°), but the reliability and validity of this 'pull-type' dynamometry has not been adequately evaluated (10, 22). The objective of this study therefore is to determine the reliability and validity of inline 'pull-type' dynamometry for measuring peak isometric knee extensor torque in patients following ACLR. We hypothesise that inline dynamometry is a reliable and valid measure of peak isometric knee extensor torque when performed at 60-70° knee flexion, using Iso-ED as the gold-standard reference.

## 5. OBJECTIVES

### 5.1 Primary Objective

To determine the reliability (inter and test-retest) and validity of the KForce Link inline dynamometer for measuring peak isometric knee extensor torque in patients following ACLR.

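### The primary objective promises inter-rater and test-retest reliability in ACLR patients, but every such measurement is taken in 20 healthy staff

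*Combined protocol and SAP*

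**What the plan says.** Section 5.1 gives the primary objective as the "reliability (inter and test-retest) and validity of the KForce Link inline dynamometer for measuring peak isometric knee extensor torque in patients following ACLR". The population phrase governs both reliability and validity, and both kinds of reliability are named.

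Three other places pair reliability with the same patients: the study title ("for measuring peak knee extensor torque in patients following anterior cruciate ligament (ACL) reconstruction"), a sentence in the synopsis narrative ("for measuring peak knee extensor torque in patients following ACL reconstruction") and the objective in section 4 ("for measuring peak isometric knee extensor torque in patients following ACLR").

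The synopsis narrative then describes the reliability study differently: "healthy volunteers will be assessed by two assessors (inter-rater) at the index testing session, with testing repeated by one assessor one week later (test-retest"). Sections 6.1, 6.3.1 and 7.1 agree that the reliability participants are healthy, and 6.1 and the synopsis table set their number at 20. Section 6.3.2 requires that this cohort has had no lower limb surgery.

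The 44 ACLR patients enter the validity study only. Section 6.1 has Assessor A use the inline device and Assessor C use Iso-ED. The synopsis adds "No follow up required for validity study".

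Section 9.1 plans ICC, SEM and MDC for reliability without naming a population. For validity it plans an ICC and Pearson correlation between the two devices.

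**The concern.** The objective and the design describe reliability in two different populations. Reliability statistics depend on the sample tested. The SEM in 9.1 is computed from the sample's SD and ICC, so it reflects how consistently those people exert maximal effort and how repeatably the assessor sets them up, as well as the gauge. People with a reconstructed knee may differ from healthy staff on both between-person spread and within-person consistency.

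The synopsis says the results will help decide whether the device "can be recommended as a reliable and valid means of measuring knee extensor torque in clinical practice", and section 4 describes that practice as including rehabilitation monitoring and return-to-play decisions after ACLR. Section 9.1 presents the MDC as the threshold for a significant change. With 5.1 naming ACLR patients and 9.1 naming nobody, a healthy-staff MDC stands as the answer to a patient question, and a clinician could apply it to a patient as though it had been verified there.

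**Working it through.** **Step 1. Trace who supplies each inline measurement.**

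| What 5.1 needs in ACLR patients | Where it is collected | ACLR patients contributing |
|---|---|---|
| Inline readings by two assessors | Assessors A and B, healthy staff only (6.1, 7.1) | 0 of 44 |
| Inline readings repeated after seven days | Assessor A, healthy staff only (6.1, 7.1) | 0 of 44 |
| Inline compared with Iso-ED | ACLR patients (6.1, 7.1) | all 44 planned |

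Section 7.1 does mention two assessors for ACLR patients, but each uses a different device. Rater and device change together, so the comparison gives no inter-rater information on the inline device. The only ICC planned in patients is therefore a between-device ICC. Because 6.3.2 bars previous lower limb surgery in the healthy cohort, no reconstructed knee can enter the reliability data by that route either.

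**Step 2. Look for a stated figure or a bridging argument.** The sample-size calculation in 9.2 (40, raised to 44) concerns validity and does not bear on this point. The 20 for reliability has no calculation to reproduce. No section argues that healthy-adult reliability carries over to patients.

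**Step 3. Illustrate what the mismatch could mean.** The documents give no patient error for this device, so these ratios are assumptions:

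- k = patient within-person SD (SEM) divided by healthy within-person SD
- r = patient total SD divided by healthy total SD
- healthy ICC taken as 0.90

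From 9.1, SEM = SD × √(1 − ICC) and MDC = 1.96 × √2 × SEM. It follows that:

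- healthy MDC relative to patient MDC = 1/k − 1
- patient ICC = 1 − 0.10 × (k/r)²

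| k | r | Error in using the healthy MDC | Patient ICC |
|---|---|---|---|
| 1 | 1 | 0 | 0.900 |
| 0.75 | 0.75 | 1/0.75 − 1 = +33% | 1 − 0.10 × 1² = 0.900 |
| 1 | 0.75 | 0 | 1 − 0.10/0.5625 = 0.822 |
| 1.5 | 1 | 1/1.5 − 1 = −33% | 1 − 0.10 × 2.25 = 0.775 |
| 1 | 1.25 | 0 | 1 − 0.10/1.5625 = 0.936 |

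The MDC error depends only on k; the ICC depends on the ratio k/r. The two shifts are separate and should not be added. On the 9.1 scale, the same healthy ICC of 0.90 (excellent) could correspond to reasonable (0.775), good (0.822) or excellent (0.936) reliability in patients. The planned data cannot show which.

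**The case against.** The strongest reply is that nothing is hidden. The synopsis narrative, the synopsis participant row, 6.1, 6.3.1 and 7.1 all tie the reliability study to healthy people, so an attentive reader would know whose data the reliability ICC comes from. That is true, and it limits the harm. But disclosure in the methods does not bring the objective into line, and no passage narrows it.

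A second reply is that the patient phrase in the title and narrative can be read as the device's intended use, with a two-part programme beneath it. The synopsis row for the primary objective and the section 4 hypothesis indeed name no population. This reading has some force for the title. It is weak for the section 4 objective and weaker still for 5.1, which spells out both types of reliability.

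Third, section 4 cites a study reporting "excellent test-retest reliability (ICC: 0.98") after ACLR. That was a push-type device at 90° of knee flexion. Section 4 itself says pull-type dynamometry has not been adequately evaluated, so the figure does not settle the question here.

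Fourth, 6.3.3 and 6.4 exclude pain, restricted motion and effusion and screen for pain before testing. This narrows the difference between the groups but does not show equal measurement error.

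Finally, patients perform three inline efforts per leg. These could give within-session repeatability for one rater, but only the highest is analysed, and they are neither inter-rater nor seven-day data.

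**Conclusion.** The concern holds. The design cannot deliver the reliability half of 5.1 in ACLR patients: 0 of 44 have a second inline rater and 0 of 44 have a retest. This follows from the documents alone and needs no assumption. The validity half is unaffected, and the healthy-adult reliability data remain usable for what they are.

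The practical size is unknown. The range of 33% too large to 33% too small for the MDC follows from assumed ratios of 0.75 to 1.5, and the ICC examples rest on an assumed healthy ICC of 0.90. They show that the error could run in either direction, not that it does. The wording should be corrected because it changes what the trial may conclude.

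**What to change.** Reword the study title, the synopsis narrative sentence, the section 4 objective and 5.1 so that reliability is stated for healthy adults and validity for patients following ACLR. In 9.1 and in the report, label the reliability ICC, SEM and MDC as healthy-adult values not verified in ACLR patients. Where 9.1 attributes the SEM to the instrument itself, describe it instead as measurement error in healthy adults under this procedure.

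This needs no extra visit, test or analysis. It touches the title and the primary objective, so it may need approval under 12.3; the documents do not say whether it would count as substantial. The cost is a narrower claim, with inter-rater and seven-day reliability after ACLR left unknown. Keeping the objective as worded would require a second inline rater and a repeat session in patients, which is additional testing and is not proposed here.

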### 5.2 Secondary Objectives

To determine comfort levels for each device during testing, as measured with a numerical rating scale of pain (0-10).

## 6. TRIAL DESIGN

### 6.1 Summary of Trial Design

This is a prospective, cross sectional study using a within-participant, repeated measures design.

#### Reliability:

A convenience sample of 20 healthy subjects (10 legs) will be recruited from Liverpool University Hospital to determine the inter- and test-retest reliability of the inline dynamometer. The testing procedure will be standardised between assessors. Subjects and assessors will be blinded to the results until all testing is completed.

Subjects will be tested by assessors A and B at the first assessment to determine inter-rater reliability. Assessor A is a physiotherapy knee specialist with 17 years clinical experience and three years clinical experience using HHD. Assessor B is a specialist physiotherapist with 8 years clinical experience but no previous experience using HHD. The order of testing will be randomised to account for fatigue and learning effect using the random.org website (<https://www.random.org/>).

To determine test-retest reliability, measurements will be repeated by assessor A seven days after the index testing. All tests will be performed at the same time of the day, with subjects encouraged to continue their usual weekly exercise between testing sessions, but to avoid significant changes in training loads, which may affect fatigue levels and their ability to generate force.

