## **6.4 Study Procedures**

Before testing, all subjects will complete a 10-minute warm up on a stationary bike followed by three trials (50%, 75% and 100% maximal effort) to familiarise themselves with each device and to screen for pain. If pain during testing is deemed intolerable by the subject, no further testing will be performed, and the subject will be excluded from the study. A 10-minute recovery period will be used between testing on devices to avoid fatigue.

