## **7.       TREATMENT OF TRIAL PARTICIPANTS**

### **7.1       Description of Study Intervention(s)**

For the reliability study, healthy subjects will be tested by two assessors at the index testing session, with three trials performed per assessor per leg. Testing will be repeated by one examiner, one week after index testing.

For the validity study, ACL subjects will be tested by two assessors with the two different devices, with three trials performed per assessor per leg. The highest score from the three trials per device will be used for analysis.

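### Any carry-over from assessor B's index test would be counted as assessor A's test-retest error: no interval between assessors is set, and day 7 is A alone

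*Combined protocol and SAP*

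**What the plan says.** - **Index session.** Section 6.1 (Reliability): "Subjects will be tested by assessors A and B at the first assessment to determine inter-rater reliability". Section 7.1 gives the load: "healthy subjects will be tested by two assessors at the index testing session, with three trials performed per assessor per leg".
- **Order.** Section 6.1: "The order of testing will be randomised to account for fatigue and learning effect using the random.org website". Section 6.4.4 repeats this for both studies. The reliability study uses one device, so the order is most naturally that of the assessors. The allocation ratio is not stated.
- **Retest.** Section 6.1: "To determine test-retest reliability, measurements will be repeated by assessor A seven days after the index testing". Section 7.1 agrees: "Testing will be repeated by one examiner, one week after index testing".
- **Rest.** Section 6.4: "A 10-minute recovery period will be used between testing on devices to avoid fatigue". The only other rest set is 60 seconds between attempts, in the testing procedure under 6.4.
- **Analysis.** Section 9.1 plans an ICC with 95% CI, a Bland-Altman plot, SEM and MDC. It does not name the form of the ICC and has no term for order or position.

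**The concern.** A test-retest comparison should repeat the measurement under the same conditions. Here, some index readings by A come after another assessor's maximal efforts in the same session, and none of the day-7 readings do. If the earlier block changes the later reading, that change is booked as instability of the device or the subject.

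The protocol itself treats within-session effects as possible: it randomises order on account of fatigue and learning, and in the validity study it puts a rest between two blocks of the same size. Randomised order helps a comparison between two things that swap positions. A's index and day-7 readings do not swap.

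What is at stake is mainly the MDC, which 9.1 presents as the smallest change to be regarded as significant. An MDC that includes carry-over from the study's two-assessor session would be wider than the one that applies when a single clinician tests a patient.

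**Working it through.** The plan gives no calculation for the 20 reliability subjects and no order effect, so there is no figure to reproduce. The check is a variance calculation.

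**Inputs**
- From the documents: 20 subjects (6.1); three efforts per leg per assessor (7.1); A alone at day 7 (6.1, 7.1); MDC = 1.96 × √2 × SEM (9.1).
- Assumed: 1:1 order; carry-over δ on the second reading in a session; r = δ / SD_d, where SD_d is the SD of retest differences without carry-over; r = 0.5 and 1.0 as illustrations; SD in the SEM formula taken as the pooled SD of all readings, so that SEM is the square root of the error variance.

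**Step 1: exposure.** The expected number with B first is 20 × 0.5 = 10. Under simple randomisation it lies between 6 and 14 with probability 0.96.

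**Step 2: the retest difference.** Day 7 minus index = e + δ × I(A second), with P(A second) = 1/2.
- Mean shift: δ/2.
- Variance: SD_d² + δ²/4.

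If the carry-over is learning, δ is negative. The mean shift reverses, but the inflation is the same because only δ² enters.

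**Step 3: inflation of SEM and MDC.**
- Absolute agreement counts the mean shift as error. Error variance is multiplied by 1 + r²/4 + r²/4 = 1 + r²/2.
- Consistency drops the mean shift. The multiplier is 1 + r²/4.

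| r | Absolute: factor, square root | Consistency: factor, square root |
|---|---|---|
| 0.5 | 1.125, 1.061 (+6%) | 1.0625, 1.031 (+3%) |
| 1.0 | 1.500, 1.225 (+22%) | 1.250, 1.118 (+12%) |

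For a small effect, r = 0.1, the absolute-agreement factor is 1 + 0.01/2 = 1.005. Its square root is 1.0025, an inflation of about 0.25%.

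**Step 4: effect on an absolute-agreement ICC**, as ICC / (ICC + (1 − ICC) × factor).

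| ICC without carry-over | r = 0.5 | r = 1.0 |
|---|---|---|
| 0.90 | 0.90/1.0125 = 0.889 | 0.90/1.05 = 0.857 |
| 0.95 | 0.95/1.00625 = 0.944 | 0.95/1.025 = 0.927 |
| 0.98 | 0.98/1.0025 = 0.978 | 0.98/1.01 = 0.970 |

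**Step 5: what r means in torque.** SD_d = CV × √(2(1 − ICC)). With an assumed CV of 25%, r = 1.0 is a carry-over of 25% × √0.20 = 11.2% of mean torque at ICC 0.90, 25% × √0.10 = 7.9% at 0.95, and 25% × √0.04 = 5.0% at 0.98. On the same CV, with absolute agreement, a carry-over of 0, 2%, 5% and 10% of mean torque gives an MDC of 15.5%, 15.7%, 17.0% and 20.8% of the mean from ICC 0.95, and 9.8%, 10.2%, 12.0% and 17.0% from ICC 0.98.

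**Step 6: inter-rater comparison.** A minus B is shifted by +δ when A goes first and by −δ when B goes first. Under 1:1 order the expected shift is zero and the added variance is δ².

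**The case against.** The strongest reply is that nothing in the documents shows a carry-over of any size. That stands, and the following stronger readings should not be drawn from the text.

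- **That fatigue will bias the result.** A reader might infer that the MDC will certainly be wrong. The documents do not support this. Sixty-second rests, scoring the highest of three efforts, and the warm-up with familiarisation trials may all keep carry-over small, and what remains could be learning.
- **That A's reading follows six maximal efforts.** Six is the total over both legs. The outcome is per leg (6.2), so each measured leg has made three scored efforts for B.
- **That there is no rest between assessors.** The text sets no minimum interval; it does not say the gap is zero. Each assessor measures lever length (6.4.4), and positioning and zeroing also take time. Staff may apply the 10 minutes anyway, but the wording does not require it.
- **That the ICC would drop out of the top band in 9.1.** This follows only from starting at 0.90, the floor of that band. From 0.95 or 0.98 the ICC stays at 0.927 or above in Step 4. The one test-retest ICC the protocol cites, for a push-type device, is 0.98.
- **That the inter-rater mean is biased too.** Randomised order protects the mean A–B difference in expectation; only added variance remains.

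It is also fair to say that with 20 subjects an ICC of 0.90 has an approximate 95% CI of 0.77 to 0.96, so a move to 0.889 is well inside sampling error, and that an inflated MDC errs towards caution. Both points limit the severity. Neither removes the asymmetry, which is systematic and can be avoided.

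**Conclusion.** The design asymmetry is certain from the text; the size of its effect is not known. A's index reading follows B's efforts in about half of subjects (assuming 1:1 assessor order), A's day-7 reading never does, no minimum interval between assessors is specified, and the analysis has no term to separate carry-over from retest error.

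If the order effect is 0.5 to 1.0 SD of the retest differences, SEM and MDC are too large by about 6% to 22% under absolute agreement or 3% to 12% under consistency. Section 9.1 does not say which form applies. At the upper end this assumes a substantial loss of torque when the ICC is near 0.90, and a more modest one when it is near 0.98. This is a cheap improvement to the plan, not a defect that undermines the study.

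**What to change.** 1. **Section 6.4.** Extend the existing 10-minute recovery so that it also applies to the change of assessor in the reliability study.
2. **Case report form and section 9.1.** Record whether A tested first or second at the index session. Model the day-7 minus index differences with that position as a factor, and report bias, SEM and MDC from this model. An equivalent is a position-by-session term in a torque model. A main effect of position in a torque model is not enough: it shifts both sessions equally and leaves index-only carry-over in the difference.
3. **Sensitivity analysis.** Report the subjects tested by A first, about 10, descriptively only. That is too few for a stable ICC or MDC.

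The cost is about 10 minutes more per healthy subject at one visit and 1 degree of freedom. No extra visit, assessor or subject is needed. If testing has already begun, the second change still works wherever the order was kept.
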